## 9.10 Replacement of Subjects

Subjects who withdraw or are withdrawn before the first dose of randomized study drug on Day 1 of the Treatment Period may be replaced.

Subjects who withdraw or are withdrawn for nonsafety reasons during the study drug treatment periods may be replaced at Vertex's discretion.

## 10 STUDY DRUG INFORMATION AND MANAGEMENT

During the TEZ/IVA Run-in Period, study drug refers to TEZ/IVA and IVA.

During the Treatment Period, study drug refers to VX-445/TEZ/IVA and matching placebo, TEZ/IVA and matching placebo, and IVA.

### 10.1 Preparation and Dispensing

Study drug may be dispensed only under the supervision of the investigator or an authorized designee and only for administration to the study subjects.

### 10.2 Packaging and Labeling

Study drug tablets will be supplied in blister cards by Vertex. Study drug labeling will be in compliance with applicable local and national regulations. Additional details regarding packaging, labeling, and dispensing for study drug will be in the Pharmacy Manual.

### 10.3 Study Drug Supply, Storage, and Handling

VX-445/TEZ/IVA will be supplied as FDC film-coated tablets containing 100 mg VX-445, 50 mg TEZ, and 75 mg IVA. Matching VX-445/TEZ/IVA placebo tablets will be of similar size and appearance and contain 0 mg VX-445, 0 mg TEZ, and 0 mg IVA (Table 10-1).

TEZ/IVA will be supplied as FDC film-coated tablets containing 100 mg TEZ and 150 mg IVA. A matching TEZ/IVA placebo tablet will be of similar size and appearance and contain 0 mg TEZ and 0 mg IVA (Table 10-1).

IVA will be supplied as a film-coated tablet containing 150 mg IVA (Table 10-1).

Blister cards must be stored under conditions noted in the Pharmacy Manual. The investigator, or an authorized designee (e.g., a licensed pharmacist), will ensure that all investigational product is stored in a secured area, under recommended storage conditions, and in accordance with applicable regulatory requirements. To ensure adequate records, all study drugs will be accounted for via the drug accountability forms as instructed by Vertex.

**Table 10-1 Study Drug: Strength/Dosing Form/Route**

Drug Name, Dosing Form, Route	Strength
VX-445/TEZ/IVA, FDC tablet, oral	
VX-445	100 mg
TEZ	50 mg
IVA	75 mg
VX-445/TEZ/IVA-matching placebo, tablet, oral	0 mg
TEZ/IVA, FDC tablet, oral	
TEZ	100 mg
IVA	150 mg
TEZ/IVA-matching placebo, tablet, oral	0 mg
IVA, tablet, oral	150 mg

FDC: fixed-dose combination; IVA: ivacaftor; TEZ: tezacaftor

### 10.4 Drug Accountability

The pharmacist or designated study site staff will maintain information regarding the dates and amounts of (1) study drug received; (2) study drug dispensed to the subjects; and (3) study drug returned by the subjects. Subjects will be instructed to return all used and unused materials associated with the study drug to the site. These materials will be retained at the site according to instructions provided by Vertex or its designee. The study monitor will review study drug records and inventory throughout the study.

If a site uses a site-specific drug accountability system and/or process, including processes associated with the destruction of returned materials, the process must be documented and approved by Vertex. The study monitor must review the drug accountability documentation on a regular basis. The study monitor will promptly communicate to Vertex any discrepancies he/she is unable to resolve with the site.

### **10.5 Disposal, Return, or Retention of Unused Drug**

The study site staff or pharmacy personnel will retain all materials returned by the subjects until the study monitor has performed drug accountability. The investigator will ensure that the materials are destroyed in compliance with applicable environmental regulations, institutional policy, and any special instructions provided by Vertex. Destruction will be adequately documented.

### **10.6 Compliance**

To ensure treatment compliance, the investigator or designee will supervise all study drug dosing that occurs at the site. At each visit, site personnel will review that the subject is compliant with study drug dosing and remind the subject of study drug dosing requirements. Compliance will also be assessed by ongoing study drug count.

If a subject demonstrates continued noncompliance of study drug dosing despite educational efforts, the investigator should consider discontinuing the subject from the study.

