##### **9.1.5.2 Discontinuation During the Treatment Period**

Subjects who prematurely discontinue study drug treatment during the Treatment Period will continue to complete all scheduled study visits following completion of the ETT Visit, as

detailed in [Table 3-2](#). These subjects will complete an ETT Visit and Safety Follow-up Visit (as applicable; see [Section 9.1.5](#)).

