## 9.9 Removal of Subjects

Subjects may withdraw from the study at any time at their own request. Subjects may be withdrawn from study drug treatment at any time at the discretion of the investigator or Vertex for safety, behavior, noncompliance with study procedures, or administrative reasons. If a subject has been withdrawn from study drug treatment, the subject will continue to be followed, provided that the subject has not withdrawn consent (and assent, as applicable).

In addition, a subject must be discontinued from study drug treatment if the subject meets any of the following criteria:

- Has a screening *CFTR* genotype that does not confirm study eligibility if a previous *CFTR* genotype laboratory report was used to establish eligibility. These subjects must be discontinued from the study (Section 8.1)
- Meets any of the stopping (discontinuation) criteria (Section 9.8)
- Becomes pregnant (Section 11.5.7.2)

Subjects who discontinue study drug treatment should return for study assessments, as noted in Section 9.1.5.2.

If a subject does not return for a scheduled visit, reasonable effort will be made to contact the subject. In any circumstance, reasonable effort will be made to document subject outcome. The investigator will inquire about the reason for withdrawal, request that the subject return all unused investigational product(s), request that the subject return for an ETT Visit and Safety Follow-up Visit, if applicable (see Section 9.1.5), and follow up with the subject regarding any unresolved AEs.

If the subject withdraws consent or assent for the study, no further assessments will be performed. Vertex may retain and continue using the study data and samples after the study is over, and may use the samples and information in the development of the study compound, and for other drugs and diagnostics, in publications and presentations, and for education purposes. If the subject withdraws from the study, the study data and samples collected will remain part of the study. A subject will not be able to request the withdrawal of his/her information from the study data. A subject may request destruction of the samples collected from him/her during the study as long as those samples can be identified as his/her samples.

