9.3.1.2 Primary Analysis

The primary analysis will be performed using a mixed-effects model for repeated measures (MMRM) with the absolute change from baseline at each post-baseline visit as the dependent variable. The model will include treatment group, visit, and treatment-by-visit interaction as fixed effects, with continuous baseline ppFEV₁, age at Screening (<18 versus ≥18 years of age), and CFTR modulator use at Screening (yes versus no) as covariates. The model will be estimated using restricted maximum likelihood. Denominator degrees of freedom for the *F*-test for fixed

effects will be estimated using the Kenward-Roger approximation². An unstructured covariance structure will be used to model the within-subject errors. If the model estimation does not converge, a compound symmetry covariance structure will be used instead. Conditional on the observed data and covariates, missing data will be assumed to be missing at random; no additional imputation of missing data will be performed.

The primary result obtained from the model will be the estimated treatment difference through Week 24 (defined as the average of Weeks 4, 8, 16, 24). The least squares (LS) mean estimate with a 2-sided 95% CI and a 2-sided P value will be provided. The treatment difference at each post-baseline visit, obtained from the model, will also be provided.

The LS mean (with SE) obtained from the MMRM analysis at each post-baseline visit up to Week 24 will be plotted by treatment group. In addition, the post-baseline raw values and the absolute change from baseline at each post-baseline visit up to Week 24 will be summarized descriptively (n, mean, SD, median, minimum, and maximum).

The primary analysis will include all available CFQ-R RD data obtained at clinic and at home. An additional analysis using data before the outbreak of COVID-19 (defined as March 2, 2020) may be performed, if the CFQ-R RD data before COVID-19 are inconsistent with CFQ-R data during COVID-19. In addition, similar additional analysis using the CFQ-R RD data obtained at clinic only may be performed, if the CFQ-R RD data obtained at home due to COVID-19 are inconsistent with the CFQ-R RD data obtained at clinic. Such additional analysis results should be interpreted with caution due to reduced sample size.

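### Protocol 10.6 suggests taking persistently noncompliant subjects out of the study, which conflicts with the sections that keep subjects in follow-up after study drug stops; primary-endpoint visits could be lost for an adherence-related reason.

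*Protocol*

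**What the plan says.** Section 10.6 (Compliance) sets the trigger, "If a subject demonstrates continued noncompliance of study drug dosing despite educational efforts", and the response: "the investigator should consider discontinuing the subject from the study". The object is the study, not study drug.

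Section 9.9 (Removal of Subjects) allows the investigator or sponsor to withdraw a subject from study drug treatment "for safety, behavior, noncompliance with study procedures, or administrative reasons". It then states: "If a subject has been withdrawn from study drug treatment, the subject will continue to be followed", on condition that consent (and assent, where applicable) has not been withdrawn. The only study-level discontinuation it requires is for a screening genotype that does not confirm eligibility.

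Section 9.1.5.2 says that subjects who stop study drug early in the Treatment Period "will continue to complete all scheduled study visits following completion of the ETT Visit". Section 9.1.3 and footnote b of Table 3-2 say the same.

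Section 9.1.7 defines completion of participation. For early treatment discontinuation in the Treatment Period without withdrawal of consent, it is the latest of the Week 24, ETT or (if required) Safety Follow-up Visit. There is no category for removal by the investigator.

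On analysis, SAP Section 9.3.1.2 states: "The primary analysis will include all available CFQ-R RD data obtained at clinic and at home". No on-treatment restriction is given. The model is an MMRM on the Full Analysis Set, assumes missing at random and does not impute. Its covariates are baseline ppFEV1, age group at screening and CFTR modulator use at screening.

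**The concern.** The protocol otherwise separates stopping study drug from leaving the study, and the SAP follows it by tabulating the two discontinuations separately (Section 9.2.1). Section 10.6 crosses that line. Two sites with identical noncompliant subjects could act differently: one keeps the Week 8, 16 and 24 questionnaires coming, and the other ends them.

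The question at stake is which data exist for the primary endpoint. Visits collected after drug is stopped enter the analysis, whereas visits of a subject removed under 10.6 would never be made. The trigger is behaviour after randomisation. If adherence predicts later CFQ-R scores beyond what the observed scores and baseline covariates explain, missing at random fails for these subjects. The model would then in effect give them the course of otherwise similar subjects who stayed.

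**Working it through.** **1. The plan's own figures reproduce.** Inputs (Protocol 12.1, SAP 7.2): SD 18, difference 10, 71 completers per group, two-sided alpha 0.05, 10% dropout.
- Standard error of the difference = 18 × √(2/71) = 3.02 points.
- Two-sample t-test power (noncentral t, 140 degrees of freedom) = 90.8%; the plan states about 90%.
- Enrolment = 142 / 0.9 = 157.8, so 158, or 79 per arm. The dropout allowance is 158 − 142 = 16 subjects.

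**2. Is the conflict real?** Section 9.9 speaks of noncompliance with study procedures, and 10.6 of noncompliance with dosing, so the listed reasons do not match word for word. The follow-up sentence in 9.9, however, covers any withdrawal from study drug, and 9.1.5.2 covers any premature treatment discontinuation in the Treatment Period. Stopping drug for dosing noncompliance falls under both. The genotype exception does not help, because the Full Analysis Set excludes subjects without the intended mutation. Section 10.6, by contrast, reaches subjects who belong in that set. Nothing in the visible text reconciles the passages.

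**3. Illustrative size.** The documents give no removal rate and no effect in such subjects, so both are assumptions. Let a share p be removed in each arm. Let the retained subjects show a difference D = 10 and the removed subjects have a true difference e.
- All-subject difference = (1 − p) × D + p × e.
- Shift = D minus that = p × (D − e).
- p = 2%, e = 5: 0.02 × 5 = 0.10 points.
- p = 2%, e = 0: 0.02 × 10 = 0.20 points.
- p = 5%, e = 5: 0.05 × 5 = 0.25 points.
- p = 5%, e = 0: 0.05 × 10 = 0.50 points.

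These shares are about 3 to 8 of 158 subjects. The shifts are 0.10/3.02 = 3% to 0.50/3.02 = 17% of one standard error.

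The formula treats every visit of a removed subject as lost. The endpoint averages Weeks 4, 8, 16 and 24, so removal after Week 8 loses two of four visits and roughly halves the range, to 0.05 to 0.25 points. The model also conditions on the earlier scores.

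**4. Direction.** Write g for the amount by which the model's implied mean for removed subjects exceeds their true mean in an arm. The shift is then p(active) × g(active) − p(control) × g(control). With equal p this is the formula in step 3. Baseline is taken on TEZ/IVA after the run-in, so poor adherers in the TEZ/IVA arm may worsen from baseline too, and losing them flatters the control. If the control term is the larger, the shift is toward no difference. The documents fix none of these four quantities.

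**5. Power.** Three to 8 removals fit within the 16-subject allowance. If instead they raised total loss from 10% to 15%, 79 × 0.85 = 67 per arm would remain and power would be 89.1%.

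**The case against.** The best defence is that this is a loose phrase in the drug-management chapter, outweighed by four consistent provisions (9.1.3, 9.1.5.2, 9.9 and Table 3-2 footnote b), with 9.1.7 offering no route for investigator removal. Section 10.6 says only that the investigator should consider the step, and only after educational efforts have failed. The SAP plainly expects poor adherers in the data: it summarises compliance below 80% on the Full Analysis Set (9.2.6) and treats it as a potential important protocol deviation, not as an exclusion (9.2.7). Section 9.10 allows nonsafety withdrawals to be replaced, and the illustrated shifts are small beside a 3-point standard error.

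Most of this stands, and it limits the weight of the point. It does not remove the conflict: 10.6 is the section a site would consult about a noncompliant subject, and its words lead out of the study. Replacement adds a new subject but does not recover the outcomes of the one removed.

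A reader might infer more: that primary data will be lost selectively and the treatment effect overstated. The documents do not support that. The step is discretionary, no removal rate is given, visits before removal stay in the analysis, and poor adherers can be lost from either arm.

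**Conclusion.** The contradiction is real and unresolved, and it bears on whether primary-endpoint data are collected. The supportable claim is that visits of Full Analysis Set subjects could be lost for an adherence-related reason that the primary model does not include. The size and direction of any resulting bias are unknown. The illustrated 0.1 to 0.5 points is not a bound: it rests on an assumed 2 to 5% removal, equal in both arms, a true difference of 0 to 5 points in those removed, and loss of all their visits. No material loss of power is shown.

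The visible SAP text has no analysis under a different missing-data assumption; its additional primary-endpoint analyses concern COVID-19 timing and location. Part of Protocol 12.3.3.1 is redacted, so this is not a finding that none was planned. This is a minor point, worth acting on because the remedy costs almost nothing.

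**What to change.** Reconcile Section 10.6 with Sections 9.9, 9.1.3 and 9.1.5.2 so that a subject acted on for noncompliance keeps all scheduled assessments unless consent or assent is withdrawn, and add a cross-reference to 9.1.5.2. Leave any decision about study drug as it is now. Sections 9.9 and 10.6 could also describe noncompliance in the same terms.

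The cost is a one-phrase protocol clarification and a note to sites. The visits are already in Table 3-2 for subjects who stop study drug, and the SAP needs no change because its primary analysis already takes all available CFQ-R data.

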### **10.7 Blinding and Unblinding**

This will be a double-blind study.

#### **10.7.1 Blinding**

All subjects (and their parents/caregivers/companions), site personnel (including the investigator, the site monitor, and the study team), and members of the Vertex study team will be blinded to the treatment codes.

Individuals who may be unblinded include only the following:

- Any site personnel for whom this information is important to ensure the safety of the subject in the event of a life-threatening medical emergency
- Any site personnel for whom this information is important to ensure the safety of the subject and her fetus in the event of a pregnancy
- Vertex Global Patient Safety (GPS) and Regulatory Affairs personnel to satisfy SAE processing and reporting regulations
- Vendor preparing the final (production) randomization list
- Vertex IWRS Manager
- Vertex Clinical Supply Chain

A limited Vertex team may be unblinded if an interim analysis (IA) is performed. Members of the limited Vertex unblinded team will not be involved in or influence the conduct of the remaining part of the study to protect the integrity of the study (Section 12.3.5.1).

#### Access to Spirometry and SwCl Results:

During the conduct of the study, the Vertex study team will not have access to the spirometry or SwCl results after the first dose of study drug in the Treatment Period.

Shortly before any planned efficacy analysis is conducted, the spirometry and SwCl data will be reviewed for data cleaning purposes by a biostatistician who does not have access to the treatment codes.

Individual SwCl test results will not be disclosed to the study sites with the exception of the screening values. Subjects and their parents/caregivers/companions should not be informed of study-related spirometry results until Vertex has determined that the study has completed (i.e., clinical study report [CSR] finalization), regardless of whether the subject has prematurely discontinued treatment.

### **10.7.2 Unblinding**

At the initiation of the study, study site personnel will be instructed on the method for breaking the blind. The unblinding method will be either manual or electronic.

#### **Unblinding of Individual Subject Treatment Assignments by Investigator for Medical Emergencies or Urgent Clinical Situations**

Unblinding of the individual subject's treatment by the investigator will be limited to medical emergencies or urgent clinical situations in which knowledge of the subject's study treatment is necessary for clinical management. In such cases, investigators will use their best judgment as to whether to unblind without first attempting to contact the medical monitor to discuss unblinding. If investigators deem it unnecessary to unblind immediately, they will first attempt to contact the medical monitor to discuss unblinding. If investigators have tried but are unable to reach the medical monitor, they will use their best judgment, based on the nature and urgency of the clinical situation, and may proceed with unblinding.

Contact information for the medical monitor (or appropriate backup) will be in a separate document.

If a subject's treatment assignment has been unblinded for a medical emergency or urgent clinical situation, the medical monitor will be notified within 24 hours of the unblinding event. The reason and the date of the unblinding will be documented clearly in the subject's study file. Information about the treatment assignment obtained from the unblinding will be maintained in a secure location with controlled access and will not be shared with Vertex, the contract research organization, or any site personnel (other than the physician treating the subject). In addition, the investigator will consider whether the clinical event that prompted unblinding will be considered an SAE, according to the regulatory definitions or criteria for SAEs, and if so, submit an SAE report to Vertex GPS or designee, per Section 13.1.2.

## **Unblinding of Individual Subject Treatment Assignments by Vertex GPS or Designee for SAEs or Safety Concerns**

Vertex GPS or designee will also unblind any SAE reports in compliance with regulatory reporting requirements. In addition, Vertex may, for matters relating to safety, unblind individual subjects at any time.

### **Unblinding: Interim Analysis**

A limited Vertex team may be unblinded if an IA is performed. Members of the limited Vertex unblinded team will not be involved in or influence the conduct of the remaining part of the study to protect the integrity of the study (Section 12.3.5.1). Regardless of the outcome of the IA, subjects (and their parents/caregivers/companions), site personnel (including the investigator, the site monitor, and the study team), and members of the Vertex study team will remain blinded until the final database lock.

## **11 ASSESSMENTS**

### **11.1 Timing of Assessments**

The timing of assessments is shown in [Table 3-1](#) and [Table 3-2](#).

### **11.2 Subject and Disease Characteristics**

Subject and disease characteristics include the following: demographics, medical history, height, and weight.

Medical history will be elicited from each subject and extracted from medical records during screening. Based on the medical history, the subject will be assessed for any disqualifying medical conditions as specified in the inclusion and exclusion criteria. The medical history will include a complete review of systems, medical and surgical histories, and any allergies.

### **11.3 Pharmacodynamics: Sweat Chloride**

SwCl samples will be collected with an approved collection device. Each collection will occur before study drug dosing (Section 9.6.1). At each time point, 2 samples will be collected, 1 from each arm (left and right). Sweat samples will be sent to a central laboratory for testing and interpretation of results. Specific instructions for the collection, handling, processing, and shipping of SwCl samples to the central laboratory will be provided separately.

See Section 10.7.1 for information about access to SwCl results.

### **11.4 Efficacy**

#### **11.4.1 Cystic Fibrosis Questionnaire-Revised**

The questionnaires provide information about demographics; general quality of life, school, work, or daily activities; and symptom difficulties (pertaining to CF).

Subjects will be asked to complete the CFQ-R in their native language, if validated translations are available. If there is no validated translation available in the subject's native language, the subject will not complete the questionnaire. Copies of the CFQ-R used will be provided in the Study Reference Manual. Validated translations of the CFQ-R, if available, will be provided for participating centers in non-English-speaking countries.

The CFQ-R will be completed before any other assessments (except signing of ICF) are performed at that visit.

Subjects who are 12 and 13 years of age at the date of informed consent will complete the CFQ-R Child version themselves, and their parents/caregivers will complete the CFQ-R Parent version, at all visits, regardless of whether the subject subsequently turns 14 years of age during the study. Subjects 14 years of age and older at the date of informed consent will complete the Adolescent/Adult version of the questionnaire themselves at all visits.

